10.3. Determination of sample size

The actual sample size of this study with respect to the analysis of persistence and safety and immunogenicity post-booster is determined by a) the sample size of the primary vaccination study MenACWY-TT-027 (108658), b) by assumptions about the enrolment rate at the Year 6-10 extension study, and c) by assumptions about the annual dropout rate. All subjects who were vaccinated in study MenACWY-TT-027 (108658) and received either MenACWY-TT vaccine, *Meningitec* or *Mencevax ACWY* in study MenACWY-TT-027 (108658) will be eligible for this study if they meet the inclusion/exclusion criteria. Six hundred and thirteen subjects (460 in the ACWY-TT group and 75 in the MenCCRM group and 78 in the MenPS group) were enrolled and vaccinated in study MenACWY-TT-027 (108658). An enrollment rate equivalent to approximately 80% of the vaccinated population in study MenACWY-TT-027 (108658) is assumed, and an annual dropout rate of 10%.

If one assumes approximately 10% of subjects dropping out of the persistence study at every visit, then one expects the following numbers of subjects to participate at each persistence time point.

- For the analysis at Year 6, it is estimated that approximately 488 subjects will be enrolled (183 in the ACWY<2, 183 in the ACWY≥2 group, 61 in the MenCCRM group and 61 in the MenPS group)
- For the analysis at Year 7, it is estimated that approximately 440 subjects will be enrolled (165 in the ACWY<2, 165 in the ACWY≥2 group, 55 in the MenCCRM group and 55 in the MenPS group)

C0921004 (MenACWY-TT-100 EXT:027 Y6,7,8,9,10, 200171)
Protocol Amendment 2

- For the analysis at Year 8, it is estimated that approximately 400 subjects will be enrolled (150 in the ACWY<2, 150 in the ACWY≥2 group, 50 in the MenCCRM group and 50 in the MenPS group)
- For the analysis at Year 9, it is estimated that approximately 360 subjects will be enrolled (135 in the ACWY<2, 135 in the ACWY≥2 group, 45 in the MenCCRM group and 45 in the MenPS group)
- For the analysis at Year 10, it is estimated that approximately 326 subjects will be enrolled (122 in the ACWY<2, 122 in the ACWY≥2 group, 41 in the MenCCRM group and 41 in the MenPS group)

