10.5.1.2. Analysis of persistence

For each Month X: The analysis of antibody persistence for MenC will be based on the ATP cohort for persistence – MenC – adapted for each time point. The analysis of antibody persistence for MenA, MenW-135 and MenY will be based on the ATP cohort for persistence – MenAWY – adapted for each time point. If, for any vaccine group, the percentage of subjects who come back for the Month X follow-up with serological results excluded from the ATP cohort is higher than 10%, a second analysis based on the Total Vaccinated Cohort Month X will be performed to complement the ATP analysis.

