10.5.2.2. Analysis of post-booster immunogenicity

The analysis of post-booster immunogenicity for MenC will be based on the Booster ATP cohort for immunogenicity - MenC. The analysis of post-booster immunogenicity for MenA, MenW-135 and MenY will be based on the Booster ATP cohort for immunogenicity - MenAWY. If, for any vaccine group, the percentage of subjects who come back with serological results excluded from the Booster ATP cohort is higher than 10%, a second analysis based on the Booster Total Vaccinated Cohort will be performed to complement the Booster ATP analysis.

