7.1.2. Analysis of Persistence

The persistence analyses will be based on the adapted ATP cohort. If for any vaccine group, at any time point, the percentage of subjects who have serological results but are otherwise excluded for the corresponding ATP cohort is higher than 10%, a second analysis based on the total enrolled cohort will be performed to complement the ATP analysis. The percentage of subjects with excluded serological results will compiled separately for the MenC ATP persistence cohort and the MenAWY ATP persistence cohort.

Different laboratories performed the rSBAs and hSBAs at different time points. rSBAs were performed either by GSK or Public Health England (PHE) (see Table 4). hSBAs were performed either by GSK or Neomed (Neomed was a GSK facility until it was spun off as an independent company) (see Table 5). Furthermore, GSK did not perform hSBAs for 2-<6 year subjects. The consequences will be described in Section 7.1.2.1, Section 7.1.2.2, and Section 7.1.3.

Table 4. Description of Laboratories Performing rSBAs by Time Point

		GSK		PHE	
Study MenACWY-	Time Point	1-<2 years	2-<11 years	1-<2 years	2-<11 years
TT-027	Baseline (Month 0)	✓	√		
	Month 1	✓	√		
TT-028	Year 1	✓	✓		
TT-029	Year 2	✓	✓		
TT-030	Year 3	✓	✓		
TT-031	Year 4	✓	✓	√	✓
TT-032	Year 5			✓	✓
TT-100	Month 78 (Year 6)			√	✓
	Month 90 (Year 7)			√	✓
	Month 102 (Year 8)			✓	✓
	Month 114 (Year 9)			✓	✓
	Month 126 (Year 10)			√	✓
	Month 127			√	√

Abbreviations: rSBA = serum bactericidal assay against *Neisseria meningitidis* using rabbit complement.

MenACWY-TT-100 (C0921004)

Table 5. Description of Laboratories Performing hSBAs by Time Point

		GS	GSK		Neomed	
Study MenACWY-	Time Point	1-<2 years	6-<11 years	1-<2 years	2-<11 years	
TT-027	Baseline (Month 0)	✓	✓			
	Month 1	✓	✓			
TT-028	Year 1	✓	√			
TT-029	Year 2	✓				
TT-030	Year 3	✓				
TT-031	Year 4	✓				
TT-032	Year 5	✓				
TT-100	Month 78 (Year 6)			√	√	
	Month 90 (Year 7)			√	√	
	Month 102 (Year 8)			✓	√	
	Month 114 (Year 9)			√	√	
	Month 126 (Year 10)			√	√	
	Month 127			✓	√	

Abbreviations: hSBA = serum bactericidal assay against Neisseria meningitidis using human complement.

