10. CHANGES FROM PLANNED ANALYSES

Please note that the changes from planned analyses to be included in the clinical study report (CSR) will be identified during the CSR review.

- The adapted ATP cohort and total enrolled cohort have been added and are explained in detail.
- Analysis of persistence for all the antigens MenA, MenC, MenW-135, and MenY will be done using the ATP cohort for persistence at Month X which will include those subjects who received a booster dose of MenC vaccine because they were non-responders after the primary vaccination in Study MenACWY-TT-027. A decision was made to include the results of the subjects who were administered a booster dose of MenC vaccine, since the removal of the results of these subjects from the analysis for persistence of MenC would result in the over estimation of the persistence of MenC.
- The new statement is "who have available assay results for at least 1 of 3 antigens (MenA or MenW-135 or MenY) at Month X." has been modified to "who have available assay results for at least 1 of 3 antigens (MenA or MenW-135 or MenY) or for MenC (for subjects who had not received MenC vaccine because they were non-responders during the persistence phase of Study MenACWY-TT-027 please see Section 7.1 of the SAP) at Month X".

MenACWY-TT-100 (C0921004)

For subjects who received MenC vaccine because they were suboptimal responders during the persistence phase of the MenACWY-TT-027 study, the persistence results for MenC will be replaced by half the cutoff in order to reflect the immunogenicity of the subjects, had they not been revaccinated.

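### The total-cohort analysis depends on a 10% exclusion count that ignores why subjects were excluded. This matters most for the booster MenC cohort, which drops subjects revaccinated for suboptimal response.

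*Protocol*

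**What the plan says.** - **Persistence, protocol.** Protocol 10.5.1.2 bases the analysis on the ATP cohorts. The complementary analysis, on the total cohort, runs only when, in at least one arm, "the percentage of subjects who come back for the Month X follow-up with serological results excluded from the ATP cohort is higher than 10" percent.
- **Persistence, SAP.** SAP 7.1.2 keeps the threshold, applies it at any time point, counts MenC and MenAWY exclusions separately, and changes the comparator: "a second analysis based on the total enrolled cohort will be performed to complement the ATP analysis".
- **Booster.** Protocol 10.5.2.2 uses the same device, a second analysis if "the percentage of subjects who come back with serological results excluded from the Booster ATP cohort is higher than 10" percent. SAP 7.2.2 repeats it. The comparator is the Booster Total Vaccinated Cohort.
- **MenC revaccination, persistence.** SAP Section 10 retains subjects revaccinated with MenC vaccine, "since the removal of the results of these subjects from the analysis for persistence of MenC would result in the over estimation" of MenC persistence. SAP 8.1 sets their later persistence MenC results, including Month 126, to half the cutoff. Neither step depends on the trigger.
- **MenC revaccination, booster.** SAP 6.2.3 (Protocol 10.4.2.3) excludes from the Booster ATP-MenC cohort anyone given MenC or MenACWY conjugate vaccine for suboptimal MenC response since the primary dose. SAP 8.1 makes no adjustment to post-booster MenC titres. SAP 7.2.2.1 tabulates Months 126 and 127.

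**The concern.** A count limits how many subjects can be missing from the ATP result. It does not limit how different they are. Ten percent excluded for reasons unrelated to titre is harmless, while a smaller fraction excluded because of low titres is not. SAP Section 10 applies this reasoning to MenC persistence and corrects for it whatever the count. Two places do not get that treatment.

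1. **Booster MenC.** The subjects dropped were identified as suboptimal responders, so their exclusion is outcome-related by definition. Below the threshold, no total-cohort booster table is planned.
2. **Persistence, other exclusions.** These are unplanned meningococcal vaccine during TT-100, immune-modifying treatment or conditions, and carry-over from earlier ATP cohorts. The SAP 8.1 rule names only MenC revaccination in the TT-027 persistence phase. Under Protocol 5.7.5, investigators receive titres and group allocation at each persistence time point, so revaccination during TT-100 is possible.

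The longitudinal model in SAP 7.1.3 does not fill the gap. It uses ATP titres only and models log titre, not percentages.

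**Working it through.** **Inputs.**
- Group sizes, Protocol 10.3: at Year 6 "it is estimated that approximately 488 subjects will be enrolled (183 in the ACWY<2, 183 in the ACWY≥2 group" and 61 per control group; at Year 10 "it is estimated that approximately 326 subjects will be enrolled (122 in the ACWY<2, 122 in the ACWY≥2 group" and 41 per control group.
- Seropositivity, Protocol 1.2: 78.6%, the Year 5 W-135 and Y figure for ACWY≥2. The documents give no control-group rate, so its use there is an assumption.
- Response among the excluded: not in the documents. Zero is taken as the bound and half the ATP rate as a milder case.

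**The plan's own figures.** Clopper-Pearson limits reproduce Table 17 on every legible limit. For example, N=183 at 80% gives 73.2 to 85.3, and N=41 at 80% gives 65.1 to 91.2.

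**Formulas.** N is the number returning with serology, k the largest whole number with k/N ≤ 10%, n = N − k, and x the whole number nearest 0.786n.
- ATP percentage p = x/n.
- Total-cohort percentage if all excluded are seronegative = x/N.
- SE = sqrt(p(1 − p)/n).
- Gap between ATP and excluded needed for a 1 SE shift = SE/(k/N).

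| N | k | ATP | Total | Shift (points) | SE (points) | Shift/SE | Gap for 1 SE (points) |
|---|---|---|---|---|---|---|---|
| 183 | 18 | 130/165 = 78.8% | 130/183 = 71.0% | 7.7 | 3.2 | 2.4 | 32 |
| 122 | 12 | 86/110 = 78.2% | 86/122 = 70.5% | 7.7 | 3.9 | 1.95 | 40 |
| 61 | 6 | 43/55 = 78.2% | 43/61 = 70.5% | 7.7 | 5.6 | 1.4 | 57 |
| 41 | 4 | 29/37 = 78.4% | 29/41 = 70.7% | 7.6 | 6.8 | 1.1 | 69 |

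Taking the stated sizes as ATP counts instead, with exactly 10% excluded and an ATP rate of 80%, the last column becomes about 30, 36, 51 and 62.

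**Milder case.** If the excluded are half as often seropositive, the shift halves to about 3.8 or 3.9 points: 1.2 SE at N=183, 1.0 at N=122, 0.7 at N=61 and 0.6 at N=41.

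**Control groups.** At N=41, if one of the four excluded is seropositive, the total is 30/41 = 73.2% and the shift is 5.2 points, or 0.8 SE. Exceeding 1 SE there requires all four to be seronegative.

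**Which exclusions could produce this.**
- *W-135 and Y persistence:* not MenC revaccination, because Protocol 10.4.1.3 and SAP Table 1 keep those subjects in the MenAWY cohort.
- *MenC persistence:* not revaccination in the TT-027 persistence phase, if SAP 6.1.2 and Section 10 govern.
- *Booster MenC, Month 126:* here the all-seronegative case is what SAP 8.1 imputes to subjects revaccinated in the TT-027 persistence phase, since half the cutoff counts as seronegative. At the Year 5 MenC rate for ACWY<2 (77.6%), with N=122 and 12 such subjects excluded, 85/110 = 77.3% against 85/122 = 69.7%, a shift of 7.6 points. The documents do not state how many were revaccinated.
- *Booster MenC, Month 127:* neither size nor direction can be derived, because titres are unadjusted and no post-booster rate is given.

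**The case against.** A reader might infer that primary MenC persistence is inflated by dropped poor responders, or that no planned analysis addresses outcome-related exclusion. The documents do not support either. SAP 8.1 and Section 10 retain the subjects revaccinated in the TT-027 persistence phase at half the cutoff, whatever the percentage excluded.

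A reader might also take the 7.7-point shift as an estimate of bias in the W-135 and Y percentages. It is only a bound. The one exclusion that the documents tie to outcome does not reach those serogroups. Nothing suggests that the remaining exclusions are all seronegative, and an unplanned vaccine would more plausibly raise titres.

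Further points against stand in part:
- **The trigger is broad.** Any one group suffices, and 5 of 41 (12.2%) would trip it. SAP 7.1.2 also allows any time point and counts the two persistence cohorts separately. That the check could appear at some visits and not others follows from the protocol's visit-by-visit wording, and is less clear under the SAP.
- **Exclusions are not hidden.** SAP 7.1.2 compiles the percentage excluded, and individual listings are released. Month 126 MenC on the persistence cohort also gives an indirect contrast with the booster cohort. None of this gives the effect on a percentage or GMT at Month 127.
- **The total cohort is not the truth.** It can include subjects given the wrong primary vaccine or boosted by other vaccines. A difference from ATP is not by itself bias in ATP.
- **All analyses are descriptive** (Protocol 10.6). This lowers the severity, but the percentages and GMTs are still what the study reports.

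**Conclusion.** The point holds in limited form and is minor. The 10% condition ignores the reason for exclusion, and no unconditional total-cohort analysis of the percentages or GMTs is planned in the text of either document. It bears most directly on the booster MenC results at Months 126 and 127, which omit known poor responders. For persistence it is confined to exclusions that the half-cutoff rule does not cover.

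The size is a bound of about 7.7 points near 79% seropositivity. It assumes the largest non-triggering exclusion, all excluded subjects seronegative, and the group sizes of Protocol 10.3. In the ACWY groups, a 1 SE shift still needs a gap of roughly 30 to 40 points. In the control groups near 79%, it needs near-complete outcome dependence. The number revaccinated and the titres of the other excluded subjects are not in the documents, so the actual shift could be negligible.

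**What to change.** 1. In Protocol 10.5.1.2 and 10.5.2.2 and SAP 7.1.2 and 7.2.2, delete the threshold. Always report percentages and GMTs on the Total cohort at Month X, and on the Booster Total Vaccinated Cohort at Months 126 and 127, beside ATP. Give the numbers excluded by reason and group.
2. Flag revaccinated subjects in those tables. State in SAP 8.1 that the half-cutoff replacement applies to their persistence MenC titres in the total-cohort tables too, including after revaccination during TT-100. Raw post-revaccination titres would not recover the unboosted percentage.
3. Show MenC booster response with and without the flagged subjects. An imputed Month 126 value set against an unadjusted Month 127 titre would make response easier to reach.
4. Reconcile SAP Table 1, which excludes unplanned meningococcal vaccines from the MenC persistence cohort without exception, with SAP 6.1.2 and Section 10, which retain the revaccinated subjects. Correct the cross-reference in SAP 6.1.2 to Section 7.1, since the rule is in 8.1. Use one name for the comparator, which is the Total Vaccinated Cohort Month X in Protocol 10.5.1.2, the Total cohort at Month X in Protocol 10.4.1.1, and the total enrolled cohort in SAP 7.1.2.

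The cost is SAP and protocol wording, reruns of existing table programs, and more tables in the annex reports. The total-cohort result should be labelled supportive, not an unbiased replacement for ATP.

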10.5.1.2.1. Within group analysis

For each treatment group, at each blood sampling time point, for each antigen assessed:

- Geometric mean antibody titres (GMTs) with 95% CIs will be tabulated.
- Percentages of subjects with titres above the proposed cut-offs with exact 95% CIs will be calculated.
- The distribution of antibody titres will be tabulated and also presented using reverse cumulative curves.

10.5.1.2.2. Between group analysis

An exploratory evaluation of the differences in the immune response at approximately 78, 90, 102, 114 and 126 months after the primary vaccination will be performed in terms of:

- Differences in the percentage of subjects with rSBA titres ≥1:8 and ≥1:128 and hSBA titres ≥1:4 and ≥1:8 between the ACWY≥2 and MenPS (primed) groups, with their standardized asymptotic 95% CIs for the four serogroups and the differences in the percentage of subjects with rSBA-MenC titres ≥1:8 and ≥1:128 and hSBA-MenC titres ≥1:4 and ≥1:8 between the ACWY≤2 and MenCCRM (primed) groups with their standardized asymptotic 95% CIs.
- Ratio of GMTs between the ACWY≥2 and MenPS groups for the four serogroups and the ratio of MenC GMTs between the ACWY≤2 and MenCCRM (primed) groups, with their standardized asymptotic 95% CIs. This will be performed using an Analysis of Variance (ANOVA) model on the logarithm₁₀ transformation of the titres using the vaccine group and age stratum as covariates.

Modelling prediction

In order to complement the descriptive analyses of observed persistence per time point and minimize the bias that may have occurred due to the loss to follow-up after the vaccination, a longitudinal analysis will be performed at the last persistence time point before booster vaccination for rSBA-MenA, C, W-135 and Y and/or hSBA-MenA, C, W-135 and Y.

More details on the modeling predication that will be done will be further described in the Statistical Analysis Plan (SAP).

10.5.1.3. Analysis of safety (Persistence epoch)

At each persistence time point, all reported SAEs related to vaccination and any event related to lack of vaccine efficacy since the last persistent time point the subject participated in up to each persistence visit in the current study will be described in detail in a retrospective manner.

10.5.2. Post-booster analyses

10.5.2.1. Analysis of demographics/baseline characteristics

Demographic characteristics of each study cohort will be tabulated: age (in years) at booster vaccination, gender and geographic ancestry.

The mean age [in years] (at the booster time point [with the range and standard deviation]) as well as the proportion of males and females and of each geographic ancestry will be calculated and presented by group.

The distribution of subjects among the study sites will be tabulated as a whole and per group.

10.5.2.2. Analysis of post-booster immunogenicity

The analysis of post-booster immunogenicity for MenC will be based on the Booster ATP cohort for immunogenicity - MenC. The analysis of post-booster immunogenicity for MenA, MenW-135 and MenY will be based on the Booster ATP cohort for immunogenicity - MenAWY. If, for any vaccine group, the percentage of subjects who come back with serological results excluded from the Booster ATP cohort is higher than 10%, a second analysis based on the Booster Total Vaccinated Cohort will be performed to complement the Booster ATP analysis.

10.5.2.2.1. Within group analysis

For each treatment group, at each blood sampling time point (Month 126 and Month 127), for each antigen assessed:

- GMTs with 95% CIs will be tabulated.
- Percentages of subjects with titres above proposed cut-offs and booster response (M127) with 95% CIs will be calculated.
- The antibody titres will be tabulated and also presented using reverse cumulative curves.

10.5.2.3. Analysis of post-booster safety

The primary analysis will be performed on the Booster Total Vaccinated Cohort and, if more than 10% of the enrolled subjects are eliminated from the Booster ATP cohort for safety a second analysis will be performed on the Booster ATP cohort for safety to support the analyses of the Booster Total Vaccinated Cohort.

For each treatment group, after the booster vaccination administered at Visit 5:

The percentage of subjects with at least one local adverse event (solicited and unsolicited), with at least one general adverse event (solicited and unsolicited) and with any adverse event during the 4-day (Days 0-3) solicited follow-up period will be tabulated with exact 95% CI. The same calculations will be performed for symptoms rated as grade 3 and for symptoms related to vaccination.

The percentage of subjects reporting each individual solicited local (any grade, grade 3, medical advice) and general (any grade, grade 3, related, grade 3 and related, medical advice) adverse event during the 4-day follow-up period (Days 0-3) after vaccination and its exact 95% CI will be tabulated. Occurrence of fever will also be reported per 0.5°C cumulative increment as well as the percentage of subjects with oral temperature

>39.5°C. Additionally, large injection site reactions will be described in detail.

The verbatim reports of unsolicited symptoms will be reviewed and the signs and symptoms will be coded according to the MedDRA Dictionary for Adverse Reaction Terminology. The percentage of subjects with unsolicited symptoms within 31 days post vaccination (Days 0-30) and its exact 95% CI will be tabulated by group and by MedDRA preferred term. Similar tabulation will be done for grade 3 unsolicited symptoms, for unsolicited symptoms possibly related to vaccination and for grade 3 unsolicited symptoms possibly related to vaccination.

The number and percentage of subjects who experienced serious adverse events and new onset of chronic illness within one month following vaccination will be tabulated with exact 95% CI.

The percentage of subjects using concomitant medication (any medication, any antipyretic/analgesic, any antipyretic/analgesic taken prophylactically, respectively) during the 4-day and 31-day follow-up periods (Days 0-3 and Days 0-30, respectively) after vaccination will be summarized.

10.6. Interpretation of analyses

All the analyses will be descriptive with the aim to characterise the immunogenicity within and between study groups.

10.7. Conduct of analyses

Any deviations or changes from the original statistical plan outlined in this protocol will be described and justified in the final study report.

10.7.1. Sequence of analyses

The persistence analysis will be done in stepwise fashion after the persistence time points for Months 78, 90, 102, 114 and 126 as soon as results are available.

The analysis of immunogenicity, safety and reactogenicity will be done after the booster time point as soon as results are available for Visit 5 and Visit 6.

The analysis will be done on a validated and frozen database. The persistence analyses will be done on as clean as possible data.

The analysis for each time point will be reported in separate annex clinical study reports in a cumulative manner. The final report containing all persistence, post-booster, and ESFU endpoints will be done on fully cleaned data.

